15.2.1 Major Stroke

A Major Stroke is to be defined as an increase of 5 or more in NIH Stroke Scale from baseline score and a Modified Rankin Score of ≥ 3 .

Note: If NIH ≥ 4 at enrollment, any change ≥ 5 is considered a major stroke. If Rankin ≥ 3 at enrollment, and change ≥ 1 is considered a major stroke .

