16.3 Statistical Methods

The pre-procedure observations will serve as the *baseline* values for calculating post procedure changes from baseline. Tabulations of summary statistics, graphical presentations, and statistical analyses will be performed using SAS software version 9.2 or higher. The statistical analyses will be based on data pooled across *Sites* in aggregate; a secondary tabulation will be prepared separately for the US and Non-US sites. Continuous demographic parameters, such as the age of the patient at the time of enrollment, will be summarized for the Per-Protocol population using descriptive statistics (N, mean, median, standard deviation, minimum and maximum value, and 95% 2-sided confidence limits). Continuous demographic parameters will be compared among the 3 levels of physician training and experience using a 1-factor (physician training [1, 2 or 3]; physician experience [participation in ROADSTER 1 or no participation in ROADSTER 1]) analysis of variance model. Contrast statements will be used to evaluate the individual pair wise comparisons (Level 1 vs. Level 2, Level 1 vs. Level 3, and Level 2 vs. Level 3; participation in ROADSTER 1 vs no participation in ROADSTER 1). Categorical demographic parameters, such as gender, will be summarized as a proportion of the Per-Protocol population using Clopper-Pearson 95% 2-sided confidence limits. The categorical demographic parameters will be compared using a Mantel-Haenszel test stratified on physician level of training (1, 2, or 3) and separately by physician experience (participation in ROADSTER 1 vs no participation in ROADSTER 1). Additionally, a generalized linear model (PROC GENMOD) will be used to evaluate the main effect of physician level of experience, specifying the distribution as either binomial or multinomial. Clinical and high risk factors will also be summarized as a proportion of the Per-Protocol population with Clopper-Pearson 95% 2-sided confidence limits. In addition to the overall summary of the individual factors, separate summaries will be generated by physician experience and level of training. Comparisons will be made among the 3 levels of physician training and physician experience (participation in ROADSTER 1 vs no participation in ROADSTER 1), depending on the type and distribution of the parameter.

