Data obtained during the neurological examination, including data from the NIH Stroke Scale, Modified Rankin Scale and Cranial Nerve Palsy Assessment will be summarized at each time point using descriptive statistics. Separate summaries will be generated by level of physician training and experience and compared using a 1-factor (physician level of training [1, 2 or 3]) and a 1-factor (experience: participation in ROADSTER 1 vs. no participation in ROADSTER 1) analysis of variance model. Contrast statements will be used to evaluate the individual pair wise comparisons (Level 1 vs. Level 2, Level 1 vs. Level 3, and Level 2 vs. Level 3).

Specific algorithms for imputing missing or partially missing dates will be discussed in the SAP. Derived data will be identified in the individual patient data listings. Imputed data for dates will not

be incorporated into the case report form datasets. Imputed data for dates will be used in the preparation of the derived datasets.

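### Section 16.3 compares neurological scores between non-randomised physician groups by 1-factor ANOVA, with no baseline term, no stated response variable, and no exact method for rare cranial nerve events

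*Combined protocol and SAP*

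**What the plan says.** Section 16.3 covers the neurological examination, "including data from the NIH Stroke Scale, Modified Rankin Scale and Cranial Nerve Palsy Assessment". These data "will be summarized at each time point using descriptive statistics". Training levels are then "compared using a 1-factor (physician level of training [1, 2 or 3"]), and a second 1-factor model uses "experience: participation in ROADSTER 1 vs. no participation in ROADSTER 1) analysis of variance model". Pairwise tests among training levels follow: "Contrast statements will be used to evaluate the individual pair wise comparisons (Level 1 vs. Level 2, Level 1 vs. Level 3, and Level 2", the last pair being the second level against the third. No covariate appears in either model, and the response variable is not stated.

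The same section opens by making the pre-procedure observations the baseline "values for calculating post procedure changes from baseline". A baseline value therefore exists, but its use in these ANOVAs is not specified.

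Four other places bear on the point:

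- The protocol summary admits both symptomatic and asymptomatic patients.
- Section 15.2.1 foresees patients who start with a deficit: "If NIH ≥ 4 at enrollment, any change ≥ 5 is considered a major stroke".
- Section 16.1.1 says that the mix of physicians by training and experience is not controlled.
- Section 16.2 makes differences between physician groups one of the aims of hypothesis testing.

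**The concern.** Patients are not randomised to physicians. If one training level treats more symptomatic patients, its patients may have higher NIH Stroke Scale and Rankin scores before the procedure. An unadjusted comparison of later scores would attribute that difference to training or experience. It would also lose power for new deficits, because stable pre-existing deficits add to the residual variance.

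Cranial nerve palsy raises a different problem. Almost every value is zero, so the ANOVA residual variance is tiny. If a group is small, one event shifts its mean by many standard errors, and the F and t approximations are not valid for such data.

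At stake is whether the p-values attached to physician training and experience, a declared interest of this study, can be believed for the neurological safety data.

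**Working it through.** **Plan's own figure.** The plan gives no figure for this analysis. The one calculated limit in section 16, the exact lower limit for 534/600, reproduces at 86.22% and is not in question.

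**Inputs.** N = 600 is from the protocol summary and section 16.1.1. The documents give no group sizes, baseline deficit rates, event rates or pre/post correlations. All of these are assumptions below.

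**Problem 1: baseline differences, raw score as response**

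*Closed form, normal scores.* Let the 30-day score equal baseline plus independent noise, with pre/post correlation ρ and no physician effect. The SD of the 30-day score is then 1/ρ baseline SDs. One level, of size m, starts d baseline SDs higher, which is ρd SDs of the 30-day score. The F test on (2, 597) df, critical value 3.01, has noncentrality λ = [m(N−m)/N](ρd)². Example: m = 200, d = 0.2, ρ = 0.7 gives 133.3 × 0.14² = 2.61 and a rejection rate of 28%.

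| d | m = 200, ρ 0.7 to 0.9 | m = 30, ρ 0.7 to 0.9 |
|---|---|---|
| 0.2 | 28-44% | 9-13% |
| 0.3 | 57-80% | 16-23% |
| 0.5 | 96-100% | 37-56% |

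Simulation gives similar values: 30-45%, 61-77% and 97-100% with 200 per level, and 10-12%, 14-23% and 33-60% with 480/90/30. ANCOVA on baseline and ANOVA on change both stay at about 4-6%.

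*Simulation, sparse scores.* A more realistic model takes about 25% of patients with a non-zero baseline and 3% with a new deficit. Several score distributions were tried.

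- Equal baselines: raw-score ANOVA rejects about 5%, as it should.
- Deficit shares 20/25/30%, no true effect: raw-score ANOVA rejects about 15-33%, baseline-adjusted analysis about 4-5%, ANOVA on change 4-5%.
- Deficit shares 15/25/40%: raw-score ANOVA rejects 53-97%. ANOVA on change rejects 4-5%, but 11% if some baseline deficits recover.
- Power for true new-deficit rates of 2/5/8%, 200 per level: raw score 25-43%, baseline-adjusted 59-62%, change 60%, chi-square on any worsening 71%.

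**Problem 2: one rare event**

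Put one event in a group of size m and zeros elsewhere. Then SS between = 1/m − 1/600 and SS within = 1 − 1/m.

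*Three-level test:* F = [(1/m − 1/600)/2] / [(1 − 1/m)/597].

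- m = 30: 0.015833/0.001619 = 9.78, p = 0.0001
- m = 85: F = 3.05, p = 0.048
- m = 86: F = 3.01, p = 0.050
- m = 200: F = 1.00, p = 0.37

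*Two-level experience test:* F = (1/m − 1/600) / [(1 − 1/m)/598].

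- m = 123: F = 3.90, p = 0.049
- m = 180: F = 2.34, p = 0.13

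So one event reaches p<0.05 overall only in a group of at most 85 (14%) by training or 123 (about 20%) by experience.

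*Level 1 vs Level 3 contrast, groups 450/120/30, event in Level 3:* t = (1/30) / √[0.001619 × (1/450 + 1/30)] = 0.03333/0.007588 = 4.39, p = 0.00001. Fisher's exact p is 30/480 = 0.06.

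*One event in each of Levels 1 and 3:* the residual mean square is 1.96444/597 = 0.003291, so t = 0.03111/0.01082 = 2.88, p = 0.004. Fisher's p is 1 − (450 × 449)/(480 × 479) = 0.12.

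*Individual contrasts* can cross 0.05 in a somewhat larger group than the overall test. With the remaining patients split equally, m = 100 gives contrast p = 0.038 where the overall p is 0.082. At m = 120 the contrast p is 0.068. With 200 per level it is 0.22.

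*Average type I error* of the overall test at event rates of 0.2-2% is 1-5% with equal groups, 5-8% with 480/90/30, and 6-12% with 500/80/20 or 540/40/20.

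**Does one remedy serve both?** No. With one 10-point jump in a group of 20 or 30 and little background change, ANCOVA still gives p<0.05 in 96-100% of runs.

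**The case against.** The strongest reply is that the plan never says raw scores are analysed. Section 16.3 provides for changes from baseline, section 15.2 defines stroke by change, and the phrase about time points governs the descriptive summaries. If change is the response, most of the false-positive excess goes and power matches the adjusted analysis. This stands as far as it goes. A reader might infer that the plan commits to a biased analysis, and the documents do not support that. They leave the response open, and a model described as 1-factor has no covariate under either reading.

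A reader might also infer that any single cranial nerve event will look significant. It will not. With 450/120/30, one event falls in the smallest group only 30/600 = 5% of the time if there is no effect. In Level 1 it gives contrast p = 0.77. Five events split 3/1/1 give contrast p = 0.12. The average type I error is only mildly off unless groups are very uneven. But group sizes are uncontrolled. The 30% cap on earlier ROADSTER sites limits sites, not patients, so small groups cannot be excluded.

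Nor do the documents support a claim that the study's main safety findings are compromised. The primary endpoint and the listed secondary endpoints, including the cranial nerve injury rate, are dichotomous and do not use this ANOVA. Suspected strokes and cranial nerve injuries are adjudicated separately.

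Two further replies are weaker. Section 16.1 defers details to a SAP, but section 16.3 already names the model, and a SAP that follows it would carry the problem forward. Section 16.1.1 doubts how informative the physician-group estimates will be, which is a reason not to attach unreliable p-values to them.

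**Conclusion.** The concern holds in qualified form and is worth acting on, as a secondary matter. The plan names unadjusted 1-factor ANOVAs for ordinal or sparse neurological data in non-randomised groups and leaves the response unspecified.

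1. On the raw-score reading, modest baseline imbalance (20/25/30%) gives about 15-33% false positives instead of about 4-5%, with lower power for new deficits. On the change reading, most of this goes, with some residual excess if baseline deficits recover.
2. For cranial nerve palsy, a single event misleads only in a small group: about 85 of 600 or fewer by training (somewhat more for an individual contrast) and about 123 or fewer by experience. It does not mislead with balanced groups.

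These are separate faults with separate remedies. Every rate depends on assumed score distributions, imbalances and group sizes, so the figures are ranges, not predictions for this study.

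**What to change.** In section 16.3, and in the SAP that follows it:

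- **NIH Stroke Scale and Rankin.** State the response variable. Compare physician groups with the pre-procedure score as a covariate, by ANCOVA or a proportional-odds model, or compare the proportion worsening from baseline. Because ANCOVA remains sensitive to one large jump in a small group, one of the other two options is preferable if a group turns out small. The proportional-odds model was not simulated here.
- **Cranial nerve palsy.** Replace ANOVA and its contrasts with Fisher's exact test for two groups and the Freeman-Halton extension for three.
- **Descriptive summaries.** Keep the means and other statistics at each time point as planned.

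The cost is a change of wording and minor programming. The plan already provides for the pre-procedure values, so no new data are needed. The exact test is conservative, so some power is lost for cranial nerve comparisons.

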16.4 Populations for Analysis

The Per-Protocol population is defined as patients who sign an informed consent, undergo the study procedure, independent of the success of the procedure, and with the absence of major protocol deviations. Patients who sign an informed consent, however fail to undergo the study procedure, will not be included in the Per-Protocol population. A maximum of 30 patients treated per protocol per physician can contribute to the 600 patient minimum. A physician may enroll more than 30 patients.

The primary endpoint and all secondary endpoints will be analyzed based on the Per-protocol population. All available data on the Per-Protocol patients who enrolled in the study will be included. Any subject not meeting the Inclusion/Exclusion criteria will be tabulated but not included in the primary endpoint analysis.

17 Data Collection

Data will be entered into a validated electronic data management system. Data fields in the selected electronic data management system used will be aligned such that it overlaps with the appropriate data fields for the post-approval study as derived from the ROADSTER IDE.

18 Sponsor Responsibilities

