POST-APPROVAL STUDY of TRANSCAROTID ARTERY
REVASCULARIZATION in PATIENTS with SIGNIFICANT CAROTID
ARTERY DISEASE.

The ROADSTER 2 Study

Clinical Protocol	SRM-2015-02
Version	E
Version Date	February 10, 2017

NCT02536378

Sponsored by:

Silk Road Medical, Inc.
[name]
[name]
United States of America
[contact]
[contact]

1 Protocol Summary

Title	POST-APPROVAL STUDY of TRANSCAROTID ARTERY REVASCULARIZATION in PATIENTS with SIGNIFICANT CAROTID ARTERY DISEASE. (The ROADSTER 2 Study)
Objective	The ROADSTER 2 Study is intended to evaluate real world usage of the ENROUTE Transcarotid Stent when used with the ENROUTE Transcarotid Neuroprotection System by physicians of varying levels of training and previous experience with the transcarotid technique.
Study Design	The ROADSTER 2 Study is an open label, single arm, multi-center post-approval Study for the treatment of patients at high risk for adverse events from carotid endarterectomy who require carotid revascularization and who are eligible for treatment with a combination of the ENROUTE Transcarotid Stent System and the ENROUTE Transcarotid NPS.
Enrollment	A minimum of 600 patients treated per protocol. Enrollment will be an entirely new cohort of patients. Additional follow-up on subjects from the ROADSTER IDE will not be included. A maximum of 30 patients per physician will be included in the first 600 patients. A physician may enroll more than 30 patients.
Investigation Site Locations	A minimum of 30 and up to a maximum of 100 sites in the United States. A maximum of 5 sites in the European Union. No more than 30% of the sites will be sites that previously enrolled in the ROADSTER study.
Primary Endpoint	The rate of procedural success through 30 days following stent implant.
Secondary Endpoints	The following secondary endpoints will be assessed 0 to 30 days: 
 ▪ Acute device success ▪ Technical success ▪ Rate of cranial nerve injury ▪ Rate of cardiac death ▪ Rate of neurological death ▪ Rate of hierarchical ipsilateral stroke, death and MI ▪ Rate of hierarchical ipsilateral stroke, death and MI by symptom status ▪ Acute device, technical and procedural success by physician experience ▪ Acute device, technical and procedural success by physician training level ▪ Acute device, technical and procedural success by enrollment quartile

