16.1.1 Sample Size Calculation

The sample size for this clinical investigation is based on the rate of procedural success within 30 days of the stent implant. The observed rate of procedural success in the ROADSTER 2 Study will be compared to an *a priori* threshold of 85% derived from the ROADSTER Study. The

rationale for an 85% threshold is based on the lower bound of the 2-sided 95% exact binomial confidence intervals of the procedural success rates from the ROADSTER Lead-In Phase (91.0%, 95% CI 81.52%, 96.64%) and the ROADSTER Pivotal Phase (95.7%, 95% CI 90.97%, 98.42%). Given that the majority of sites that will participate in the ROADSTER 2 Study will not have participated in the ROADSTER IDE, the procedural success rate must consider outcomes from early enrollment. With an observed rate of procedural success >89% in the ROADSTER 2 Study, the results will be significant with a minimum of 600 patients, meaning the lower bound of the 2-sided 95% exact binomial confidence interval will exceed 85%. Deterministically, if 534 patients of the 600 total cases (89%) were classified as a procedural success within 30 days of the stent implant, the exact 95% lower binomial confidence limit would be 86.22%.

Estimates for the 3 categories of physician level of training and experience (yes/no) will be summarized. However, given the distribution of physicians by level of training and experience will not be controlled for in this clinical investigation, it is indeterminate how informative the estimates will be.

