16.2.1 Primary Endpoint

The primary endpoint for the study is the rate of procedural success through 30 days following stent implant. The derivation of the endpoint for the primary analysis of the primary endpoint will consider all patients who undergo the procedure and in the absence of a major protocol deviation, i.e., the Per Protocol population. Patients who exit the study prior to the 30 day post-procedure evaluation who meet the definition of a procedural success based on their last observation will be counted in the analysis as a procedural success. Secondary analyses of the primary endpoint will consider alternative methods of imputation; the details of these supplemental analyses will be described in the Statistical Analysis Plan.

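### All endpoints are planned in the Per-Protocol population only, so a real-world-usage study would not show how its exclusions affect the result

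*Combined protocol and SAP*

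**What the plan says.** Section 16.4 sets the analysis population for every endpoint: "The primary endpoint and all secondary endpoints will be analyzed based on the Per-protocol population". Its members must give consent and "undergo the study procedure, independent of the success of the procedure, and with the absence of major protocol deviations". Section 16.2.1 repeats this for the primary endpoint, which uses "all patients who undergo the procedure and in the absence of a major protocol deviation, i.e., the Per Protocol population". For eligibility failures, Section 16.4 adds: "Any subject not meeting the Inclusion/Exclusion criteria will be tabulated but not included in the primary endpoint analysis".

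The only supplemental analyses named for the primary endpoint are in Section 16.2.1: "Secondary analyses of the primary endpoint will consider alternative methods of imputation". Their details are left to the SAP.

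The baseline description follows the same population. Section 16.3 summarises demographics for Per-Protocol patients, and "Clinical and high risk factors will also be summarized as a proportion of the Per-Protocol population".

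The objective in the Protocol Summary is that the study "is intended to evaluate real world usage of the ENROUTE Transcarotid Stent", used with its companion neuroprotection system by physicians of differing training and experience.

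**The concern.** In routine use some treated patients have major deviations or turn out not to meet the criteria. The plan removes the first group from every endpoint, including the safety endpoints in Section 16.2.3: cardiac death, neurological death, cranial nerve injury, and the stroke, death and MI composite. It removes the second group at least from the primary endpoint.

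Exclusion may be related to outcome. Section 15.1 has the Clinical Events Committee (CEC) review major deviations that affect patient safety, and the supplied text does not require deviations to be classified without knowledge of outcome.

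If excluded patients do worse, the Per-Protocol rates overstate success and understate harm. If they do equally well, nothing changes. No analysis planned in the supplied text would say which case applies, or by how much.

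**Working it through.** **Inputs from the plan.** Minimum of 600 Per-Protocol patients; threshold 85%; success judged by the lower limit of the 2-sided 95% exact binomial interval (Sections 16.1.1 and 16.2.2). The example in Section 16.1.1 is: "if 534 patients of the 600 total cases (89%) were classified as a procedural success". Prior success rates are 91.0% (lead-in) and 95.7% (pivotal).

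**Inputs assumed.** The number of excluded treated patients, M, and the number of successes among them, s. The documents give neither.

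**Formula.** For x successes in n patients, the Clopper-Pearson lower limit L(x, n) is the 0.025 quantile of a Beta(x, n − x + 1) distribution. The result passes if L exceeds 85%. The all-treated result uses x + s successes in 600 + M patients.

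**Step 1: the plan's figure.** L(534, 600) = 86.22%, as stated. The smallest passing count is 528/600 (88.0%, L = 85.13%); 527/600 gives 84.95%.

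**Step 2: effect on the rate.** If a share w = M/(600 + M) is excluded, Per-Protocol success is p and success among the excluded is q, then the Per-Protocol rate exceeds the all-treated rate by w(p − q). With 30 excluded at 50% and p = 89%, this is 30/630 × 39 = 1.86 percentage points, taking 89.00% to 87.14%.

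**Step 3: effect on the lower limit.**

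| Per-Protocol result | 30 excluded, 50% success | 60 excluded, 70% success | 60 excluded, 80% success |
|---|---|---|---|
| 534/600 (89%), L = 86.22% | 549/630, 84.27%, fails | 576/660, 84.49%, fails | 582/660, 85.47%, passes |
| 546/600 (91%), L = 88.42% | 561/630, 86.34%, passes | 588/660, 86.46%, passes | not needed |
| 574/600 (95.7%), L = 93.71% | 589/630, 91.27%, passes | 616/660, 91.15%, passes | not needed |

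**Step 4: break-even.** With 630 treated, 554 successes are needed (L = 85.13%; 553 gives 84.96%). With 660 treated, 580 are needed (L = 85.14%; 579 gives 84.98%). Subtracting the Per-Protocol successes gives the successes needed among the excluded:

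| Per-Protocol result | 30 excluded (4.8% of treated) | 60 excluded (9.1% of treated) |
|---|---|---|
| 528/600 | 26 (86.7%) | 52 (86.7%) |
| 534/600 | 20 (66.7%) | 46 (76.7%) |
| 546/600 | 8 (26.7%) | 34 (56.7%) |
| 574/600 | 0; L(574, 630) = 88.61% | 6 (10%) |

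**Step 5: smaller exclusions.** From 534/600, seven excluded patients can all fail and the result still passes (534/607, 85.12%); eight failures bring it below the threshold (534/608, 84.96%). Twelve excluded at 50% success give 540/612 and 85.41%, which passes.

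**The case against.** Use of the Per-Protocol population is consistent across Sections 16.2.1, 16.3 and 16.4, and nothing is contradictory. Failed procedures without a major deviation stay in the denominator. The following points can be made against the concern.

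- **Unseen text.** Section 16.1 calls itself an outline and defers details to a SAP, and Sections 2 to 14 are not in the supplied text. An all-treated analysis could be specified there. This stands as a limit on the claim. However, Section 16.2.1 describes the deferred supplemental analyses as imputation methods, and Section 16.4 assigns all secondary endpoints to Per-Protocol without any such deferral.
- **Meaning of real-world.** The objective stresses variation among physicians, and the design row restricts the study to eligible patients. That supports keeping ineligible subjects out of the primary test. It does not explain the removal of eligible treated patients with other major deviations.
- **Ineligible subjects.** They are expressly removed only from the primary endpoint, and the Per-Protocol definition does not mention eligibility. Their removal from the safety endpoints holds only if ineligibility counts as a major deviation, which the supplied text does not say. This narrows the safety concern for that group.
- **Partial handling.** Ineligible subjects are tabulated, and the CEC reviews safety-related deviations. Neither provision promises an endpoint estimate that includes the excluded patients.
- **Magnitude.** The failing scenarios rest on assumed exclusions and start from the 89% example. This is correct, and the tables show where the conclusion does not change.

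**Conclusion.** The concern holds. As written, the plan tests the 85% threshold and reports all secondary endpoints only in treated patients without a major deviation. It names no wider analysis set and no comparison with those left out.

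The true effect cannot be computed, because neither the number of exclusions nor their outcomes are given. Under the assumed scenarios, the conclusion is sensitive near the plan's 89% example: with 30 excluded, at least 20 must succeed, and with 60, at least 46. It is robust near the prior pivotal rate. This is an inexpensive improvement to reporting rather than an error in the plan, and nothing in the documents shows that excluded patients do worse. The sample-size arithmetic is not in dispute.

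**What to change.** In Sections 16.2.1 and 16.4:

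- Define an All-Treated population: consented patients in whom the study procedure was started, regardless of deviations or eligibility findings.
- Report the primary endpoint with its exact 95% interval against 85%, and all safety endpoints, in that population beside the Per-Protocol results.
- List the outcomes and baseline risk factors of excluded patients by reason for exclusion.
- Require major deviations to be classified without knowledge of outcome, before database lock, and state whether ineligibility counts as one.

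Per-Protocol can remain the primary population, and the 600-patient target can stay.

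The cost is protocol and SAP wording and one more set of tables. CEC review under Section 15.1 covers events during enrolment and is not limited to Per-Protocol patients, so adjudicated strokes and cranial nerve injuries should exist for excluded patients. That section does not list MI or death as such, so the sponsor should confirm that 30-day data on every component are collected for these patients. The drawback is a second success rate to report, possibly slightly lower.
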